5.6 Soft tissue thickness

At visit 1 or visit 2 (start of surgery), depending on local practice and requirements, soft tissue thickness should be measured. For the ATB System, the skin thickness should not exceed 6 mm to ensure optimal retention and system performance. The measurement should be performed in the centre of the marked coil position. For complete instruction see the surgery guide ⁵.

5.7 Surgery

The surgery, performed at visit 2, does not take account for any particular circumstances or factors relevant to an individual patient or case. Other surgical approaches and variations are practiced and may be more appropriate in certain patient cases. After considering all relevant circumstances, factors and information in each case, the appropriate surgical procedure is determined by the responsible investigator exercising independent medical judgment. Complete information is found in the surgery guide⁵.

During surgery the following variables should be collected:

- Surgery time (time between first incision to last suture)
- Bone polishing/removal at the actuator site (yes/no)
- BI300 Implant length (3mm/4mm)

- Location of BI300 Implant (mm from the ear channel), measured horizontally and vertically). Distance from BI300 to receiver/coil (centre to centre). An alternative option to preoperative measurements with a ruler, is to take a lateral skull radiography postoperatively and measure the distance between the implant receiver magnet and the BI300.
- Type of anaesthesia (general/local)
- Soft tissue reduction (yes/no)
- Surgical incision type (C-shaped flap is anterior based for an anterior actuator position or posterior based flap is considered for a more posterior actuator position or other incision type)

At visit 3, approximately 2 weeks after surgery sutures should be removed.

5.8 Intraoperative Test system (IOTS)

At visit 2, in the end of the surgery procedure, the IOTS test should be performed. The test takes approximately two minutes to perform, and the software provides the user with an unambiguous test result regarding device integrity prior to closing and suturing the surgical site. It is crucial that the staff during surgery follow the instruction for use¹⁰. The software used for the IOTS is installed on a lap-top provided by the Sponsor. The software collects data from transducer of the implant and will make the Sponsor gain understanding of the behaviour and performance of the transducer once implanted on a recipient. IOTS data will be saved on the lap-top until study is ended when it will be transferred to the Sponsor in a coded way.

5.9 Sound Processor fitting

The Baha Fitting Software 4.0 SR2⁸ will be used at visit 1 when the fitting procedure should be performed for the Baha BP110 Power Sound Processor as a reference device.

The Osia Fitting Software 1.02⁷ will be used to adjust the investigational device sound processor settings for a specific subject. This will happen during Visit 4 when tests will be performed, and throughout the study. The fitting software will be installed on a lap-top provided by the Sponsor, and the fitting-data will be saved on the lap-top until study is ended when it will be transferred to the Sponsor in a coded way.

The Digital Link Calibration (e.g. coil-to-coil measurement) that is a step in the connection step in the Osia Fitting Software, should be performed at each occasion that the software is being used to fit or fine tune the device to optimize the performance of the device throughout the study. This will also provide an indication of the soft tissue thickness.

For the sound processors Individual Stable Gain (e.g. feedback measurements as part of the Fitting Software) the Feedback Analyser should be performed at each occasion that the software is being used to fit or fine tune the device to optimize the performance of the device throughout the study. For the Investigational device this data will be collected, saved and eventually transferred to the Sponsor for analysis.

5.10 Magnet choice

At visit 4 (sound processor fitting) the most suitable magnet should be selected for the sound processor to be tested, and the instruction for use⁵ should be followed. It is important that the strength is not too weak or too strong. There are 7 different strengths, starting from ½ to 6. During the following

visits the choice of sound processor magnet should be checked. There may be a need to decrease or increase the strength depending on the subject's preference.

5.11 Bone Conduction (BC) Direct

BC Direct is a tool in the Baha Fitting Software (current version) to establish the unmasked bone condition threshold with tones presented through the sound processor. At Visit 1, BC Direct data shall be collected with the Baha BP110 Power Sound Processor on a Softband and shall be used to calculate the fitting (settings) of the sound processor for the Softband test. BC Direct measurements (as part of the Osia Fitting Software) will also be performed at visit 4 to visit 8 when the subject is using the investigational device. BC thresholds obtained at the following frequencies will be recorded; 250, 500, 750, 1000, 1500, 2000, 3000, 4000, 6000 Hz.

5.12 Simultaneous bilateral

In the case of a subject receiving simultaneous bilateral ATB systems one of the treatment ears will be selected as the investigational ear for efficacy purposes. Speech in noise performance will be documented for the second ear alone and bilaterally. However, efficacy outcomes for the investigational ear only will be pooled with the outcomes measures made for the unilaterally implanted subjects. Investigational ear choice will be as judged by the responsible investigator prior to surgery. Patient-reported outcomes (APHAB, SSQ and HUI), will be collected post-surgery in a bilateral situation. Safety-related information, including adverse events, will be collected and reported for each ear receiving the ATB system.

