2.2 Blinding

No blinding will be used in this clinical investigation.

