5.4 Baseline characteristics

During visit 1 a number of baseline characteristics will be recorded;

- Treatment ear (indicate left or right or both. In case of both, indicate side for hearing tests)
- Type of hearing loss: (Conductive, Mixed or SSD)
- Aetiology: (chronic) infection, tumour, trauma, malfunction, otosclerosis, other

- Current hearing aid (yes/no, specify model, side and years of hearing aid use, reason for change)
- Previous experience from amplified sound through properly fitted amplification (yes/no, specify type, years of aid in use, when stopped use, reasons stop using)
- Has the subject previously been suggested a bone conduction hearing implant (BCHI) solution (yes/no, reason for rejection)

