5.5 Audiogram

Unaided audiometric threshold measures (including both air- and bone conduction thresholds) should demonstrate that the subject has a conductive, mixed hearing loss or single-sided sensorineural deafness and meets the audiological inclusion criteria.

An existing audiogram may be used as long as it has been completed during the last six months, and contains all the required relevant frequencies (250, 500, 750, 1000, 1500, 2000, 3000, 4000, 6000 and 8000Hz). The subject's pre-operative Pure Tone Average PTA4 (mean of 500, 1000, 2000 and 4000Hz) should be computed and recorded to ensure the subject meets the inclusion criteria.

If an audiogram is older than 6 months or does not contain the required frequencies, a new will be performed at Visit 1. Frequencies required for air conduction thresholds are 250, 500, 750, 1000, 1500, 2000, 3000, 4000, 6000 and 8000Hz. Bone conduction thresholds are 250, 500, 750, 1000, 1500, 2000, 3000, 4000 and 6000Hz. Contralateral masking should be used if needed, and according to local practice. The hearing care professional shall always record the unmasked threshold and record the masked if applicable.

Audiograms for bone conduction thresholds will also be performed at Visits 6, 7, and visit 8 to monitor hearing thresholds postoperatively.

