10.3 Sample size calculation

10.3.1 Sample size calculation for the primary efficacy analysis

In order to achieve 90% power to detect a clinically significant difference of 10 dB in free-field hearing thresholds or 10 dB SNR between the unaided situation and the ATB System at the 3 months visit with Fisher's non-parametric permutation test for paired observations, one-sided test with significance level 0.025, on the ITT population 11 (PTA-4) and 13 (SNR) evaluable subjects are needed. The sample size was calculated using simulation on study id CBAS5675 (Cochlear 2017) data which used the simulated ATB system on Mixed/Conductive subjects. The within subject SD for change Unaided to ATB in PTA4 was 9.5 dB and 11.3 SNR. Since significant result want to be detected in both arms (SSD and Conductive/Mixed) 13+13=26 subjects should be included in the investigation.

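### In subjects implanted on both sides, the ear that supplies the efficacy data is left to unblinded judgement, which can inflate the PTA4 and SNR benefit: a minor point with a simple fix

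*Protocol*

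**What the plan says.** Protocol 5.12 deals with subjects who receive two systems at the same operation. One ear is named the investigational ear: "Investigational ear choice will be as judged by the responsible investigator prior to surgery". In the analysis, "efficacy outcomes for the investigational ear only will be pooled with the outcomes measures made for the unilaterally implanted subjects". On the other ear, the section says "Speech in noise performance will be documented for the second ear alone and bilaterally" but names no visits. No free-field PTA4 is scheduled for the second ear.

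Protocol 5.4 lists the treatment ear among the Visit 1 baseline data and adds: "In case of both, indicate side for hearing tests". It does not refer to 5.12. On the audiogram, Protocol 5.5 says: "An existing audiogram may be used as long as it has been completed during the last six months". Protocol 2.2 says: "No blinding will be used in this clinical investigation".

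The SAP is silent on bilateral subjects:
- Section 3.1.2 lists treatment ear as right or left only.
- Section 3.3.4 takes the Visit 1 audiogram from both sides and relabels the sides as test and non-test.
- Section 4.10.1 plans one sensitivity analysis of the primary variable, on complete cases.
- Section 6 declares no departure from the protocol.

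**The concern.** Both ears are implanted whichever is named, so the label does not change the treatment. It decides which of two possible changes is used for PTA4 and SNR. The person who assigns it is not blinded, needs no stated reason, and has the hearing data that make up the unaided side of the comparison.

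Both primary endpoints are changes from the unaided preoperative result (Protocol 10.2.1). An ear with a poorer unaided result or a larger air-bone gap may have more room to improve. If such ears are preferred, bilateral subjects contribute a favourable ear, while unilateral subjects contribute the only one they have. Each subject is his or her own control, so no concurrent arm would share the selection and cancel it. At stake are the estimated benefit and, in a small arm, the one-sided 0.025 error rate.

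**Working it through.** **1. The plan's own figure.** Protocol 10.3.1 states: "one-sided test with significance level 0.025, on the ITT population 11 (PTA-4) and 13 (SNR) evaluable subjects are needed". The inputs there are 90% power, a difference of 10 dB, and SDs of change of 9.5 dB (PTA4) and 11.3 (SNR, read here as dB). The paired normal approximation is n = (SD × (1.960 + 1.282) / 10)².
- PTA4: (9.5 × 0.3242)² = 9.5, so 10 (stated 11).
- SNR: (11.3 × 0.3242)² = 13.4, so 14 (stated 13).

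Both are within one subject. The plan simulated from pilot data, so an exact match is not expected. These SDs are used below. They come from Mixed/Conductive subjects, which is the arm mainly concerned.

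**2. What is known when the ear is chosen.** The audiogram is needed for eligibility and may predate Visit 1. Protocol 5.4 records the test side at Visit 1, whereas 5.12 only requires the choice before surgery. No section says that the choice precedes the Visit 1 free-field or speech tests, or that it is then fixed. The 3-month results are not known.

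**3. Ceiling on the selection effect.** Assume that the changes in the two ears are normal with equal means, common SD and correlation ρ, and that the ear with the larger realised change is always picked. The expected excess per bilateral subject is SD × √((1 − ρ)/π). The range of ρ is an assumption.

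| ρ | PTA4, SD 9.5 | SNR, SD 11.3 |
|---|---|---|
| 0.3 | 4.5 dB | 5.3 dB |
| 0.5 | 3.8 dB | 4.5 dB |
| 0.8 | 2.4 dB | 2.9 dB |

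Multiply by the share of the arm that is bilateral, assumed to be 10 to 40%:
- PTA4: 0.10 × 2.4 = 0.2 dB to 0.40 × 4.5 = 1.8 dB.
- SNR: 0.10 × 2.9 = 0.3 dB to 0.40 × 5.3 = 2.1 dB.

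**4. Error rate under the same ceiling.** This was simulated for PTA4 with no true change, ρ = 0.5, 100,000 replicates, and a paired t-test standing in for the permutation test. Protocol 10.3.4 sets at least 13 subjects per arm. With 50 in total, an arm could hold up to 50 − 13 = 37.

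| Arm size | 1 bilateral | 2 | 3 | 5 |
|---|---|---|---|---|
| 13 | 0.032 | 0.038 | 0.047 | 0.071 |
| 25 | 0.029 | 0.035 | 0.041 | 0.056 |
| 37 | 0.029 | 0.033 | 0.037 | 0.051 |

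The nominal rate is 0.025.

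**5. Regression to the mean.** If two truly equal ears were separated on the same noisy baseline that enters the change, the excess would be e/√π for measurement error e. That is 1.7 dB at an assumed e of 3 dB and 2.8 dB at 5 dB, per bilateral subject. For PTA4 this does not fit the schedule well: the test side is recorded at Visit 1 and no second-ear free-field PTA4 is planned. The audiogram is a separate measurement, and choosing on it does not carry its error into the free-field baseline. For SNR the route stays open, because 5.12 does not say at which visits the second ear is tested.

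**6. Which arm.** Protocol 3.1.1 defines the SSD arm by single-sided deafness, with either a good other ear or a CROS indication. Bilateral implantation should therefore fall mainly in the Conductive/Mixed arm. Each arm is tested separately (Protocol 10.5.1), so the SSD test should be largely unaffected.

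**The case against.** The strongest reply is that the choice is made before surgery, so nobody can pick the ear with the larger 3-month change. This stands. A reader might infer that each bilateral subject contributes the better of two changes, or that the reported benefit is biased upward. The documents support neither. The figures in steps 3 and 4 include noise that cannot be foreseen, so they are ceilings that no investigator could reach. Nothing in the text says that the ear with more to gain is preferred, and judgement could go either way.

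Further points stand in whole or in part:
- A poorer unaided ear need not gain more, because its aided result may be poorer too. Where it does gain more, that is a real benefit in that ear. The question is then which ear the estimate describes, and the effect is not a false one.
- Free-field and speech-in-noise tests require blocking of the non-test ear only when it is normal, near-normal or clearly better (Protocol 6.2 and 6.4). In symmetric loss the other ear may contribute, which dilutes the effect of the choice.
- The label is not purely analytic. Protocol 6.1 monitors postoperative bone conduction in the study ear.
- Section 5.12 is a contingency, and neither document expects any particular number of bilateral subjects.

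None of this supplies a criterion, a lock or a sensitivity analysis. The audiogram alone leaves room for selection on expected gain.

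**Conclusion.** The concern holds as a possibility. In simultaneous bilateral subjects, unblinded judgement decides which ear enters the efficacy analysis, without a stated criterion. The PTA4 and SNR benefit can therefore be biased upward, mainly in the Conductive/Mixed arm. Actual bias is not shown.

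The bilateral share and the between-ear correlation are assumptions, so the true size is unknown. Even the ceiling is about 2 dB or less on the arm mean against a 10 dB target. It bears more on the size of the estimate than on the conclusion. The error rate would rise materially only if several bilateral subjects fell in a small arm and the larger-gain ear were reliably picked. The point is minor, but worth correcting because the remedy costs almost nothing.

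**What to change.** - **Protocol 5.12:** replace the sentence on ear choice with a rule that leaves no discretion. For example: the investigational ear is assigned at random in the eCRF at enrolment, before any Visit 1 free-field, speech or Softband test, and is then locked. A fixed-side rule would also remove the discretion. Protocol 3.5 rules out randomisation because there is no comparator device, which does not prevent random assignment of this label.
- **Protocol 5.4:** refer to that rule when the side for hearing tests is recorded.
- **SAP 4.10.1:** add a sensitivity analysis of both primary endpoints that excludes bilateral subjects. This also covers those already enrolled. **SAP 3.1.2:** add a category for both ears, so that these subjects can be identified.

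The cost is one protocol sentence, one eCRF field and a short SAP addition, with no extra tests and no change in sample size. The downside is that the investigator loses the choice of test ear. Because the same label sets which ear has bone-conduction monitoring under Protocol 6.1, that choice is lost too. Section 6.1 should be read against the per-ear safety collection in 5.12 when the change is made.

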6 ASSESSMENTS

Assessments that will be performed during the clinical investigation is outlined in the flow chart, see section 8.

During the assessments, the signal processing of the sound processors will be harmonised according to given instructions given in the eCRF. This will also be included in the staff training at each participating centre during the site initiations.

6.1 Postoperative audiometric assessment

Bone conduction thresholds for the study ear will be monitored postoperatively, to characterize observed unaided thresholds postoperatively. These measures will occur at visit 6 (3 months postoperative) and 7 (6 months postoperative), once healing and swelling is most likely to be resolved and repeated at visit 8 (12 months postoperative). Bone conduction thresholds are 250, 500, 750, 1000, 1500, 2000, 3000, 4000 and 6000Hz. Contralateral masking should be used if needed, and according to local practice. The hearing care professional shall always record the unmasked threshold and record the masked if applicable.

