3.3.4 Audiogram

Audiogram at Visit 1, Air condition/Bone conduction, Right/Left (transferred to test side/Non test side), Unmasked/Masked for 250, 500, 750, 1000, 1500, 2000, 3000, 4000, 6000 and 8000 Hz. At 3 months visit and 12 months visit test side audiogram, bone conduction (unmasked and if needed masked) thresholds at 250, 500, 750, 1000, 1500, 2000, 3000, 4000 and 6000Hz will be collected.

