4.11.4 Audiogram

Audiogram (Air and Bone conduction), test side for 250, 500, 750, 1000, 1500, 2000, 3000, 4000, 6000 and 8000 Hz by SSD and Conductive/Mixed patients will be presented at visit 1, 6 and 8. At visit 6 and 8 is only bone conduction performed.

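### Per-ear safety data are promised for bilaterally implanted subjects, but postoperative bone-conduction thresholds are specified only for the study ear or test side

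*Protocol*

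**What the plan says.** **Protocol 5.12** covers simultaneous bilateral implantation. It confines the choice of a single ear to efficacy ("one of the treatment ears will be selected as the investigational ear for efficacy purposes") and treats safety differently: "Safety-related information, including adverse events, will be collected and reported for each ear receiving the ATB system". The only second-ear hearing test it names is speech in noise ("Speech in noise performance will be documented for the second ear alone and bilaterally").

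**Protocol 4.3 and 10.2.3** list the audiogram among the safety outcomes. In 4.3 this means bone conduction before surgery and at 3, 6 and 12 months, with no ear specified.

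**Protocol 6.1** is the operative instruction for the postoperative test: "Bone conduction thresholds for the study ear will be monitored postoperatively", at Visits 6, 7 and 8 and at nine frequencies. **Protocol 5.4** records the treated side as "Treatment ear (indicate left or right or both. In case of both, indicate side for hearing tests". **Protocol 5.5** schedules the same postoperative audiograms without naming an ear.

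**Protocol 7.2.4** makes a threshold shift from the preoperative baseline reportable as an adverse event once it is more than 15 dB HL at any one frequency.

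**SAP 3.3.4** takes both sides at Visit 1, recoded as test and non-test side. After surgery it takes one: "At 3 months visit and 12 months visit test side audiogram, bone conduction (unmasked and if needed masked) thresholds". **SAP 4.11.4** presents "Audiogram (Air and Bone conduction), test side for 250, 500" and the remaining frequencies. **SAP 3.1.2** lists treatment ear as right or left only. SAP section 6 declares no changes from the protocol.

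**The concern.** The promise in 5.12 and the instruction in 6.1 do not describe the same data. A site that follows 6.1 and names one side for hearing tests under 5.4 would take no scheduled postoperative bone-conduction threshold in the second implanted ear. An analyst who follows the SAP would have no place to put one. With treatment ear coded right or left, a second implanted ear would fall under the non-test side and could not be told apart from an unimplanted ear.

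At stake is the threshold monitoring of an ear that has had the same surgery and carries the same device as the first. The 7.2.4 rule depends on a measured threshold, and in that ear the schedule does not clearly provide one.

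**Working it through.** The plan gives no figure to reproduce on this point. The check is a comparison of the texts.

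| Question | Protocol | SAP |
|---|---|---|
| Which ears does the safety promise cover? | Each implanted ear (5.12) | No bilateral provision |
| Is the audiogram a safety variable? | Yes (4.3, 10.2.3) | Yes (3.3.4, 4.11.4) |
| Which ear is measured after surgery? | The study ear (6.1); no ear named (5.5) | Test side (3.3.4) |
| Which ear is tabulated? | Not stated | Test side (4.11.4); no second-ear table in 7.1 |
| Can a bilateral subject be identified? | Yes (5.4 allows left, right or both) | No (3.1.2: right or left) |
| Is there a second-ear baseline? | 5.5 requires air and bone thresholds | Yes, both sides at Visit 1 (3.3.4) |

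**Step 1.** The one-ear selection in 5.12 is limited to efficacy, and the audiogram is a safety variable. The per-ear promise therefore covers it.

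**Step 2.** Protocol 6.1 names a single ear. Protocol 5.5 names none, so it does not override the more specific wording of 6.1.

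**Step 3.** No other scheduled test fills the gap. Speech in noise for the second ear gives no frequency-specific threshold. BC Direct (5.11) is unmasked. Its Visit 1 values come from the BP110 on a Softband and its later values from the implant, so it has no same-method baseline. It is also not stated to be done for each ear.

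**Step 4.** Size per bilateral subject: 1 of 2 implanted ears. On the protocol schedule that is 9 frequencies × 3 visits = 27 readings not clearly required. On the SAP schedule (3 and 12 months) it is 9 × 2 = 18.

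**Step 5.** Size across the trial: the number of bilateral subjects, k, is not given. With 50 subjects the share of implants affected is k/(50 + k). Purely as an illustration, with k assumed to lie between 0 and 5:
- k = 0: 0/50 = 0%
- k = 1: 1/51 = 2.0%
- k = 5: 5/55 = 9.1%

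**The case against.** The best defence is that 5.12 is the specific rule for bilateral subjects and already requires the second-ear audiogram as safety information. On this view 6.1, whose term for the ear is undefined and differs from the one in 5.12, should be read in that light. Neither 5.5 nor the flow chart limits the ear. This is a fair reading of intent, and it supports the fix. It does not remove the conflict, because 6.1 and both SAP sections still name one side.

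Stronger conclusions are tempting, but the documents do not support them:

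- **That a hearing loss in the second ear would go unseen.** A symptomatic loss can be reported as an adverse event, extra visits are allowed, second-ear speech in noise is documented, and 7.2.4 is not itself limited to one ear or to scheduled tests. What is missing is systematic measurement and tabulation.
- **That half of a bilateral subject's exposure lies outside the safety tables.** SAP 3.3.2 counts all reported events and 4.11.2 gives numbers of events as well as subjects. A second-ear device deficiency would still register under SAP 3.3.3. Only the audiogram presentation is expressly confined to one side.
- **That numbness and device deficiency are given once per subject.** The SAP states no such unit, and protocol 6.9 describes an implant-site evaluation without restricting it to one ear.
- **That this explains the missing threshold data at the 6-month primary safety analysis.** The SAP omits the 6-month audiogram for every subject. That is a separate point.

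It is also true that the subgroup may be empty, that the safety analyses are descriptive, and that no efficacy, power or alpha result is affected.

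**Conclusion.** The inconsistency is real and sits in the current text of both documents. In any simultaneously bilateral subject, the second implanted ear's postoperative bone-conduction thresholds would not be systematically measured or tabulated, and the 15 dB rule would have no scheduled measurement to act on in that ear.

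The size is one of two implanted ears per bilateral subject. The plan gives no basis for a trial-wide figure. The conclusion assumes that the study ear in 6.1, the test side in the SAP and the investigational ear in 5.12 are the same ear. The documents do not say so, but that is the natural reading. The point is worth correcting because it concerns safety data already promised and the correction is small.

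**What to change.** **Protocol.** Reconcile 5.4, 5.5 and 6.1 with 5.12 so that bone conduction at Visits 6 to 8 covers each implanted ear, as 5.12 already promises. Use one defined term for the ear chosen for efficacy, and keep it out of the safety instructions.

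**SAP.** Add a category for both ears to treatment ear in 3.1.2. In 3.3.4 and 4.11.4, collect and present bone-conduction thresholds for each implanted ear. Show the number of implants beside the number of subjects in the safety tables.

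**Cost.** Wording changes in two documents, plus one more ear tested at three scheduled visits with equipment already in use, in bilateral subjects only. Visit 1 audiograms already cover both sides, so no new baseline is needed. If no bilateral subject is enrolled, the cost is the wording alone.
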